#### **4.4.2 Exclusion Criteria**

Subjects will not be entered in the study for any of the following reasons:

1. The subject has any serious health condition, which, in the opinion of the Investigator, would place the subject at undue risk from the study, including:
  - a. uncompensated congestive heart failure (New York Heart Association Class III or IV);
  - b. clinically significant active cardiac disease (eg, unstable angina or acute myocardial infarction within 3 months);
  - c. recently active cerebrovascular disease (eg, stroke or transient ischemic attack within 3 months);
  - d. uncontrolled hypertension, unless attributable to SLE disease activity;
  - e. uncontrolled diabetes;

- f. pancreatitis within the past 14 days prior to screening, unless attributable to SLE disease activity; if recent pancreatitis, must have normal amylase and lipase for 7 days prior to screening;
  - g. known clinically significant immunodeficiency;
  - h. substance abuse, such as alcoholism or drug abuse;
- i. history of a known peripheral neuropathy, such as mononeuritis multiplex, acute or chronic inflammatory demyelinating polyneuropathy, axonal sensorimotor neuropathies, drug-related neuropathy or neuritis, or diabetic neuropathy;

2. Subject has had recent serious or ongoing infection, or risk for serious infection, including:
  - a. active or latent tuberculosis, as suggested by chest x-ray or CT scan within the 3 months prior to screening and/or QuantiFERON-TB Gold/tuberculin purified protein derivative testing at screening (subjects with a history of latent tuberculosis with documented completed treatment by a Centers for Disease Control-recommended regimen are allowed);
  - b. known history of chronic hepatitis B or hepatitis C, as suggested by serological testing;
  - c. seropositivity for human immunodeficiency virus (HIV);
  - d. history of PML;
  - e. use of antibiotics within 2 weeks of baseline; or
  - f. live vaccinations within 8 weeks of baseline.
3. Subject has screening laboratory abnormalities of any of the following criteria:
  - a. hemoglobin < 10.0 g/dL;
  - b. absolute neutrophil count < 1500/ $\mu$ L ( $< 1.5 \times 10^9/L$ );
  - c. platelet count < 100,000/ $\mu$ L ( $< 100 \times 10^9/L$ );
  - d. alanine aminotransferase (ALT) or aspartate aminotransferase (AST) > 1.5x upper limit of normal (ULN);
  - e. serum total bilirubin > 1.5x ULN, or > 3x ULN for patients with Gilbert's syndrome;

- f. serum creatinine > 1.5x ULN or estimated glomerular filtration rate (eGFR) < 60 mL/min/1.73m^2; or
- g. serum amylase or lipase > 1.5x ULN.

4. Subject has a history of new or recurrent malignancy within the past 5 years, except basal cell carcinoma of the skin, squamous cell skin cancer, or in situ carcinoma that has been adequately treated with no evidence of recurrent disease for 12 months.
5. The subject is pregnant and/or breastfeeding.
6. The subject is unable or unwilling to complete the study protocol.
7. The subject fulfills diagnostic criteria for another rheumatic (overlap) disease that may confound clinical assessments in the study. Secondary sicca or Sjögren's syndrome, antiphospholipid antibody syndrome, and overlap with rheumatoid arthritis ("rhupus") are allowed.
8. The subject is receiving treatment with any of the following within the timeframes indicated before baseline, if not otherwise previously dosed longer term according to Inclusion Criterion 9:
  - a. corticosteroids: 2 weeks;
  - b. cyclosporin, tacrolimus, methotrexate, leflunomide, azathioprine, 6-mercaptopurine, cyclophosphamide, tofacitinib, or other Janus kinase (JAK) inhibitors: 4 weeks;
  - c. biologic therapies, including belimumab, abatacept, interleukin (IL)-6, and TNF- $\alpha$  (eg, infliximab, adalimumab, certolizumab pegol, or golimumab) antagonists: 8 weeks;
  - d. rituximab or other B cell depleting therapies: 6 months (subjects who have been exposed to B cell depleting therapies must have a normal peripheral B cell count at baseline, if not demonstrated before); or
  - e. other drugs or biologics, including investigational products: 8 weeks or 5 half-lives, whichever is longer.
9. The subject has urgent, severe SLE disease activity, which, in the opinion of the Investigator, warrants immediate immunosuppressive therapy and would not be appropriate for the study (eg, severely active neuropsychiatric SLE warranting immediate pulse corticosteroids and/or immunosuppressants such as cyclophosphamide, which makes the possibility of receiving placebo an inappropriate risk).

10. The subject has ongoing participation in another therapeutic clinical trial.
11. The subject has a known hypersensitivity to brentuximab vedotin, component thereof, or excipient contained in the drug formulation.

#### **4.4.3 Disease Diagnostic Criteria**

For participation in the study, subjects must:

- have a documented diagnosis of SLE for at least 6 months prior to screening according Inclusion Criterion 5;
- must demonstrate active SLE at screening and at baseline, as indicated in Inclusion Criterion 7; and
- have failed at least one of the treatments for SLE as listed in Inclusion Criterion 8.

#### **4.4.4 Subject Withdrawal**

All subjects are free to withdraw from participation in the study at any time, for any reason, specified or unspecified, and without prejudice to further treatment. The criteria for enrollment are to be followed explicitly. If a subject who does not meet enrollment criteria is inadvertently enrolled, that subject should be withdrawn from the study, and the Sponsor and Quintiles must be contacted.

In addition, subjects will be withdrawn from study drug and from the study in the following circumstances:

- The Investigator decides that the subject should be withdrawn. If this decision is made because of an intolerable AE or a clinically significant laboratory value, the study drug is to be discontinued and appropriate measures are to be taken. The Sponsor and Quintiles are to be notified immediately.
- The subject experiences a clinically significant worsening of SLE warranting a significant change in therapy according to the Investigator. The Sponsor and Quintiles are to be notified immediately.
- The subject experiences signs or symptoms suggestive of PML.
- The subject experiences any Grade 3 or higher infection.
- The subject experiences any Grade 3 (according to the National Cancer Institute's Common Terminology Criteria for Adverse Events [NCI-CTCAE]) or higher neutropenia (ie, absolute neutrophil count  $< 1.0 \times 10^9/L$ ), thrombocytopenia (ie, platelet count

$< 50 \times 10^9/L$ ), anemia (ie, hemoglobin  $< 8.0 \text{ g/dL}$  or transfusion indicated), or liver function test abnormal (ie, ALT or AST  $> 5x \text{ ULN}$ ) that does not correct to Grade 1 or better before the next scheduled dose of brentuximab vedotin.

- The subject experiences any Grade 3 or higher neuropathy. Dosing will be withheld for any subject who experiences Grade 2 neuropathy, but decisions to resume dosing will be made on a case-by-case basis in consultation with the Medical Monitor (see Section 5.1).
- The subject has missed more than 1 dose.
- The subject is unwilling to continue in the study.
- The subject exhibits a lack of compliance with protocol.
- The Investigator or the Sponsor, for any reason, stops the study.

Subjects who discontinue the study early will have early termination procedures performed as shown in the schedule of events (Table 3). Subjects who are withdrawn from the study will not be replaced.

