## 5.0 STUDY TREATMENTS

### 5.1 Treatments Administered

Eligible subjects will receive 4 doses of either brentuximab vedotin 0.3, 0.6, 1.2, or 1.8 mg/kg IV or matching placebo, given every 3 weeks (Days 1, 22, 43, and 64) during the treatment period.

Individual doses are based on subject weight (see Section 5.5) and will be administered as an IV infusion over approximately 30 minutes. The study drug cannot be mixed with other medications.

Dose reductions are not permitted; however, dosing will be withheld if a subject experiences Grade 2 neuropathy. Resumption of dosing will be decided on a case-by-case basis by the Medical Monitor. Subjects who experience Grade 3 or higher neuropathy or who miss more than a single dose will be withdrawn from the study (see Section 4.4.4).

Further instructions on the dose preparation and administration will be provided in the Pharmacy Manual.

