### **5.6 Blinding**

This is a randomized, double-blind, placebo-controlled study with limited access to the randomization code. Brentuximab vedotin and placebo solutions for IV administration will be identical in physical appearance. The treatment each subject will receive during the treatment period will not be disclosed to the Investigator, study site personnel, subject, Sponsor, or Quintiles. Upon request, treatment assignments will be revealed to the Investigators when the clinical study report is final. The SMC will review and evaluate blinded interim safety data after the final subject of each cohort has been evaluated at the

Day 43 visit. The data for a given cohort may be unblinded for preliminary data analyses after completion of all subjects for the cohort (Day 85 and/or Day 127).

The process for breaking the blind will be handled through the IWRS. Investigators are strongly discouraged from requesting the blind be broken for an individual subject, unless there is a subject safety issue that requires unblinding and would change subject management. Any site that breaks the blind under inappropriate circumstances may be asked to discontinue its participation in the study. If the blind is broken, it may be broken for only the subject in question and the subject must be withdrawn from the study.

The Sponsor and Quintiles must be notified immediately if a subject and/or Investigator is unblinded during the course of the study. Pertinent information regarding the circumstances of unblinding of a subject's treatment code must be documented in the subject's source documents and case report forms (CRFs).

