### **Adverse Events of Special Interest**

For this study, AEs of special interest include any treatment-emergent neuropathy and suspected cases of PML (see Section [6.3.1.3](#) for reporting of AEs). These events will be followed until significant changes return to baseline, the event stabilizes or is no longer considered clinically significant by the Investigator, the subject dies or withdraws consent, or the study is closed.

Subjects who experience a Grade 2 neuropathy will have dosing withheld (see Section [5.1](#)); subjects with Grade 3 or higher neuropathy will be withdrawn from the study (see Section [4.4.4](#)).

See Section [6.3.3](#) for additional information on PML monitoring and Section [6.3.2](#) for management of infusion reactions.

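### Protocol 4.4.4 takes subjects off the study, not only off drug, for toxicity and missed doses, so one exit visit stands in for their remaining scheduled safety visits

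*Protocol*

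**What the plan says.** Protocol 4.4.4 opens its list with the rule that "subjects will be withdrawn from study drug and from the study in the following circumstances". The toxicity and dosing entries are:

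- any Grade 3 or higher infection;
- any Grade 3 or higher neuropathy;
- Grade 3 or higher neutropenia, thrombocytopenia, anemia or ALT/AST elevation that has not recovered to Grade 1 by the next dose;
- more than one missed dose;
- an Investigator decision. Here the text adds: "If this decision is made because of an intolerable AE or a clinically significant laboratory value, the study drug is to be discontinued".

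Other sections repeat the rule. Protocol 5.1 says: "Subjects who experience Grade 3 or higher neuropathy or who miss more than a single dose will be withdrawn from the study". The special-interest part of 6.3.1.1 says that "subjects with Grade 3 or higher neuropathy will be withdrawn from the study".

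On what happens next, 4.4.4 says: "Subjects who discontinue the study early will have early termination procedures performed as shown in the schedule of events". Section 4.3.3 and Table 3 show that this is one visit, the same one that completers attend on Day 127. No off-drug visit schedule is given. Also, "Subjects who are withdrawn from the study will not be replaced".

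Section 4.4.4 also lists signs that suggest PML as a reason to leave drug and study. Section 6.3.3 handles the same event differently: it suspends dosing, sends the subject to a neurologist, and allows dosing again once PML is ruled out. If JCV is detected, drug stops for good and the subject moves to safety follow-up.

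**The concern.** Safety and tolerability is the primary objective (Protocol 3.1). Under this rule, scheduled monitoring ends early in the subjects who had toxicity. Milder toxicity can lead there too: Grade 2 neuropathy requires doses to be withheld (5.1), and a second withheld dose means study exit.

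Three uses of the data are affected.

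- **SMC.** Its Day 85 review can stop or truncate the next dose cohort (4.5). For a subject who left earlier it has the triggering event and the exit visit, but no Day 85 assessments.
- **AE tables.** Percentages use the whole Safety Population (SAP 19.1), so these subjects stay in the denominator with a shorter observation time and no allowance for it.
- **Late reporting.** Section 6.3.1.3 keeps new-onset neuropathy and suspected PML reportable to the end of a follow-up period that is not defined for a subject who leaves early.

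The PML texts give sites two instructions for a subject in whom PML is suspected and then excluded.

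**Working it through.** **Inputs.** Post-baseline schedule from Protocol 4.3.2.2 to 4.3.3 and Table 3:

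- neurological/PML examinations: Days 22, 43, 64, 85, 106, 127;
- CBC and chemistry: Days 8, 15, 22, 29, 43, 50, 64, 71, 85, 106, 127;
- ECG: Days 43 and 85;
- exit visit (4.3.3): includes a neurological examination, CBC and chemistry, but no ECG;
- doses: Days 1, 22, 43, 64.

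The documents give no figure of their own to reproduce here.

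**When exits fall.** The first dose follows randomization on Day 1, so the second missed dose can only be on Day 43 or Day 64. Grade 3 or higher neutropenia in the pivotal trials came after a median of 2 doses (2.6). The second dose here is on Day 22, so a case that has not recovered by the next dose would leave at about Day 43.

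**Visits lost.** Net loss = scheduled assessments after the exit day, minus what a separate exit visit supplies.

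| Exit | Neurological exams | CBC/chemistry draws | ECG |
|---|---|---|---|
| Day 43 | 4 − 1 = 3 | 6 − 1 = 5 | 1 − 0 = 1 |
| Day 64 | 3 − 1 = 2 | 4 − 1 = 3 | 1 − 0 = 1 |

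If the Day 43 or Day 64 visit itself serves as the exit visit, nothing is subtracted and the losses are the first numbers in each cell.

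**Time lost.** To Day 127: 127 − 43 = 84 days, or 127 − 64 = 63 days. Completers are followed for 127 − 64 = 63 days after their last dose. The shortfall against that standard is (last dose day + 63) − exit day:

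- exit Day 43, last dose Day 22: 85 − 43 = 42 days;
- exit Day 43, last dose Day 1 (Days 22 and 43 missed): 64 − 43 = 21 days;
- exit Day 64, last dose Day 43: 106 − 64 = 42 days;
- exit Day 64, last dose Day 22 (Days 43 and 64 missed): 85 − 64 = 21 days;
- exit straight after a dose on Day 43 or Day 64: 63 days.

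**What falls in the gap.** Section 2.5 gives a median neuropathy onset of 12.4 to 15.0 weeks in oncology patients: 1 + 12.4 × 7 ≈ Day 88 to 1 + 15.0 × 7 = Day 106. Those patients were on continued dosing, so this is only indicative, but it lies after either exit day.

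**How many subjects.** No exit rate is stated. One exit is 1/8 = 12.5% of a planned dose group. If the pivotal-trial rate of 20% for Grade 3 or higher neutropenia (2.6) applied at 1.8 mg/kg, 8 × 0.20 = 1.6 subjects would be expected to have the event. That counts events, not exits: only unrecovered cases leave, and the median duration was 1 week.

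**The case against.** The strongest reply is that little is lost. The triggering event is recorded, and each AE counts once per subject, so the trigger stays in the tables. Existing SAEs are followed until they resolve or stabilize, later related SAEs are reported (6.3.1.3), and neuropathy and suspected PML have their own follow-up rule (6.3.1.1). The SMC can look at neurological and other safety events whenever it sees fit, and escalation rests on Day 43 data, which an exit at Day 43 leaves intact. Number of doses received and reasons for discontinuation are reported. All of this stands and limits the point to the residue: new nonserious AEs, worsening of other nonserious AEs, later SAEs judged unrelated, and scheduled findings.

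Some stronger readings are tempting, and the documents do not support them.

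- **Safety follow-up stops at exit.** It does not; event-level follow-up continues as above.
- **Two thirds of observation is lost at Day 43** (84 of 126 days). The fraction is right as calendar time, but it is not like-for-like with the 63 days that completers get after their last dose.
- **AE rates at higher doses are biased down.** This is possible, but no exit rate by dose is given.
- **The PML texts also conflict on whether a JCV-detected subject leaves the study.** The safety follow-up in 6.3.3 is undefined and can be read as the Follow-up or Early Discontinuation visit, so this second conflict is weak.
- **Every entry in 4.4.4, and unblinding in 5.6, should become a drug-only stop.** Section 5.6 reserves unblinding for cases with a safety reason and then says "the subject must be withdrawn from the study", so it touches similar subjects. The argument here rests on the toxicity and missed-dose triggers. Non-compliance that prevents follow-up, and an Investigator's decision on other grounds, are legitimate reasons to leave.

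A fair objection to the remedy is burden. A subject stopped for anemia should not go on giving research blood in a study that may take about 700 mL (6.4.1). The fix allows for that.

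**Conclusion.** The point holds. As written, the plan ends scheduled safety observation early in subjects who had toxicity or missed doses, although the visits to follow them already exist. Per subject the net loss is 3 neurological examinations, 5 CBC/chemistry draws and 1 ECG for an exit at Day 43, and 2, 3 and 1 at Day 64, assuming a separate exit visit. Observation ends 84 or 63 days before Day 127; measured against completers' follow-up after last dose, the shortfall is 21 to 63 days in the cases worked above. The total effect depends on an exit rate that the documents do not give. The sponsor should make the change because it bears on the primary objective and costs little, not because bias has been shown.

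The PML inconsistency on resuming dosing is real: one subject cannot both be withdrawn on suspicion and be eligible to resume. It is a text correction and carries no weight in the main point.

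**What to change.** In 4.4.4, 5.1 and 6.3.1.1, make the following reasons to discontinue study drug only: Grade 3 or higher infection, Grade 3 or higher neuropathy, unrecovered Grade 3 or higher cytopenia or ALT/AST elevation, more than one missed dose, and an Investigator decision based on an AE or laboratory value. Ask these subjects to attend the remaining scheduled visits through Day 127 for:

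- AEs, concomitant medications, vital signs, physical and neurological examination, CBC and chemistry, and the Day 85 ECG;
- the noninvasive efficacy scales.

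Omit PK/PD and RNA draws where clinically inappropriate. Flag efficacy and AE data collected after drug stop or rescue therapy.

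Keep study withdrawal for withdrawn consent or unwillingness, an Investigator decision on other grounds, non-compliance that precludes follow-up, loss to follow-up (not listed now), and the study being stopped. In 6.3.1.3, define the end of the follow-up period as Day 127 for subjects who stop drug early.

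Separately, align the PML entry in 4.4.4 with 6.3.3: suspend dosing on suspicion, resume only if PML is ruled out, and stop drug permanently with continued safety follow-up if JCV is detected.

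The cost is a protocol amendment. Every drug-stopping rule stays except for suspected PML, where 6.3.3 would govern. Some subjects will decline the visits, and data after drug stop may reflect other therapy.

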#### **4.3.2.2.5 Day 29 ( $\pm 2$ days)**

Approximately 1 week following the administration of study drug (Day 29  $\pm 2$  days), blood samples for clinical laboratory assessments (CBC with differential and chemistry panel) will be collected.

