#### **4.3.2.2.6 Day 43 ( $\pm 2$ days)**

On Day 43 ( $\pm 2$  days) prior to study drug administration, the following assessments will be performed:

- BILAG, SLEDAI, CLASI, SJC/TJC, PtGP, PtGA, PhGA, HAQ-DI, SF-36, FACIT-F, and LupusQoL assessments;
- physical and neurological (PML assessment) examinations;
- measurement of vital signs (blood pressure, pulse rate, respiratory rate, temperature, and weight);
- clinical laboratory assessments (CBC with differential, chemistry panel, fasting lipid panel, urinalysis, and urine pregnancy test for WOCBP only);

(Note: The results of the CBC must be available prior to dosing and testing may be done by a local laboratory to facilitate availability of the results. In addition, a separate CBC sample for central laboratory testing should also be collected. Urine pregnancy testing will be performed locally only and results must be available prior to dosing.)

- ECG;
- collection of blood samples for PK analysis (predose and end of infusion) and antitherapeutic antibodies (predose only);

- collection of blood samples for flow cytometry, inflammatory markers, ANA, anti-dsDNA antibodies, autoantibody panel, complement studies, and RNA analysis; and
- recording of AEs/SAEs and concomitant medication use.

Following completion of predose procedures, subjects will receive either brentuximab vedotin or matching placebo as an IV infusion over approximately 30 minutes. Blood samples for PK analysis will be collected prior to and at the end of the infusion; samples for antitherapeutic antibodies will be collected prior to dosing only.

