### 6.3.5 Clinical Laboratory Evaluations

Samples will be drawn for both central and local laboratories. Local laboratory testing will include institutional standard tests for evaluating safety and making clinical decisions.

The following laboratory assessments will be performed by the central laboratory (unless otherwise specified) to evaluate safety at scheduled time points (see [Table 3](#)) during the course of the study:

- CBC with differential: hemoglobin, hematocrit, RBC count, mean corpuscular hemoglobin, mean corpuscular hemoglobin concentration, mean corpuscular volume, red cell distribution width, WBC count with 5-part differential (neutrophils, lymphocytes, monocytes, eosinophils, and basophils), and platelet count;

Note: The results of the CBC must be available prior to administration of each dose; therefore, testing at these time points may be done by a local laboratory to facilitate availability of the results. In addition, separate CBC samples at all specified time points should be collected for central laboratory testing.

- B cell count as quantified by CD19+ cells on flow cytometry, if applicable (for subjects with prior B cell depletion therapy, see [Table 3](#));
- HbA1c;
- chemistry panel: sodium, potassium, chloride, bicarbonate, blood urea nitrogen, creatinine, uric acid, albumin, eGFR, glucose, total bilirubin, direct bilirubin, AST, ALT, alkaline phosphatase, lactate dehydrogenase, amylase, lipase, and creatine phosphokinase;
- eight-hour fasting lipid panel: total cholesterol, triglycerides, high-density lipoprotein, and low-density lipoprotein;
- urinalysis: dipstick urinalysis, spot urinary protein and creatinine, and microscopic examination of the urinary sediment; and
- pregnancy test for WOCBP (Note: testing will be performed locally only and results will be available prior to dosing).

In addition, viral serology (HIV, hepatitis B surface antigen, anti-hepatitis B surface antibody, anti-hepatitis B core antibody, hepatitis C, and JCV) and tuberculosis (QuantiFERON-TB Gold or tuberculin purified protein derivative) tests will be performed at screening only.

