- c Complete blood count with differential to include hemoglobin, hematocrit, RBC count, mean corpuscular hemoglobin, mean corpuscular hemoglobin concentration, mean corpuscular volume, red cell distribution width, WBC count with 5-part differential (neutrophils, lymphocytes, monocytes, eosinophils, and basophils), and platelet count. Results must be available prior to dosing; therefore, an additional sample may be collected for local laboratory testing on Days 1, 22, 43, and 64. The predose sample on these days should still be collected for central laboratory testing.
- d B cell count for subjects with prior B cell depletion therapy, such as rituximab. Baseline testing may be omitted for subjects with normal counts at screening.
- e Chemistry panel includes: sodium, potassium, chloride, bicarbonate, blood urea nitrogen, creatinine, a albumin, eGFR, glucose, total and direct bilirubin, ALT, AST, a alkaline

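### The ALT/AST limb of the withdrawal rule is judged before the next dose, but no pre-dose chemistry result is required, so its application is not assured

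*Protocol*

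**What the plan says.** Section 4.4.4 of the protocol has one withdrawal rule with four laboratory limbs: neutrophils, platelets, hemoglobin, "or liver function test abnormal (ie, ALT or AST" above 5 times ULN). In each, a Grade 3 or higher value leads to withdrawal if it is one "that does not correct to Grade 1 or better before the next scheduled dose of brentuximab vedotin". Under Section 5.1 the doses are "given every 3 weeks (Days 1, 22, 43, and 64) during the treatment period".

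Section 6.3.5 sets the condition for the blood counts: "The results of the CBC must be available prior to administration of each dose". The notes under Days 1, 22, 43 and 64 in Section 4.3.2 and Table 3 footnote c repeat it and permit a local laboratory. The same visit notes also require the urine pregnancy result. They name nothing else.

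The chemistry panel is drawn at the same pre-dose visits. Section 6.3.5 assigns it to the central laboratory unless otherwise specified, and Table 3 footnote e lists its contents without a timing requirement. Between doses, chemistry is drawn on Days 8 and 15, then on Day 29, where "blood samples for clinical laboratory assessments (CBC with differential and chemistry panel) will be collected", and on Day 50.

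A related entry rule is Exclusion 8d: subjects previously given B cell depleting therapy "must have a normal peripheral B cell count at baseline, if not demonstrated before". Table 3 footnote d adds: "Baseline testing may be omitted for subjects with normal counts at screening".

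**The concern.** All four limbs share one decision point, the next scheduled dose, but the protocol secures the deciding evidence for only three of them. A site that follows the visit schedule exactly can infuse without knowing whether the ALT/AST limb has been met.

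The primary objective is safety and tolerability. The prescribing information in Appendix 4 (Section 5.8) reports serious hepatotoxicity, including fatal outcomes, with cases after the first dose and after rechallenge. If the limb is applied at some sites and not at others, discontinuations and liver findings by dose group partly reflect laboratory turnaround rather than the rule.

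**Working it through.** No figure in the plan is being reproduced. The check sets the rule against the laboratory schedule and counts days.

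**Step 1. Evidence secured for each limb before infusion**

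| Limb of 4.4.4 | Sample | Result required before infusion? | Source |
|---|---|---|---|
| Neutrophils, platelets, hemoglobin | CBC | Yes, local laboratory permitted | 4.3.2 visit notes, 6.3.5, Table 3 footnote c |
| ALT/AST | Chemistry panel | Not stated; central laboratory by default | 6.3.5, Table 3 footnote e |

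**Step 2. Time from the last interim chemistry to the dose**

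Inputs: interim chemistry on Days 15, 29 and 50 (each ±2 days); doses on Days 22, 43 and 64 (each ±2 days).

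Nominal gap = dosing day − last interim day. With windows, the range is the nominal gap ± (2 + 2).

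- Dose 2: 22 − 15 = 7 days; 7 − 4 = 3 to 7 + 4 = 11.
- Dose 3: 43 − 29 = 14 days; 14 − 4 = 10 to 14 + 4 = 18.
- Dose 4: 64 − 50 = 14 days; again 10 to 18.

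No chemistry is scheduled inside these gaps. The next sample is the dosing-day draw.

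**Step 3. Which elevations run into the gap**

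After the first dose, a Grade 3 or higher ALT/AST with a dose still to come can first appear on six scheduled days: 8, 15, 22, 29, 43 and 50. For Days 22 and 43 I take the next dose to be the one three weeks later.

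- Days 15, 29 and 50 (3 of 6): the only scheduled recheck is the draw on Day 22, 43 or 64 itself.
- Days 8, 22 and 43 (3 of 6): a scheduled recheck falls on Day 15, 29 or 50. If it shows Grade 1 or better, the rule is settled in time. If not, the decision again rests on the dosing-day draw.

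So the gap opens whenever the Day 15, 29 or 50 value in such a subject is above Grade 1, whichever day the elevation began. From Day 71 on there is no next dose and the limb does not arise.

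**Step 4. The B-cell count**

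The Day 1 CD19+ result decides eligibility only if the subject had prior B cell depletion and no normal count was shown before Day 1. In that case the Day 1 note in Section 4.3.2.1 does not list the result among those needed before dosing. If the subject is then found ineligible, Section 4.4.4 calls for withdrawal without replacement, at a cost of 1 of 8 active or 1 of 2 placebo subjects in that cohort.

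**The case against.** The strongest reply is that the protocol is silent on chemistry turnaround, and silence is not a bar. Section 4.4.4 asks for correction before the next dose, not for a dosing-day value, so a known unresolved Grade 3 result arguably obliges the site to obtain one. Section 6.3.5 has samples drawn for local as well as central laboratories and lets local tests guide safety and clinical decisions. Section 4.4.4 allows withdrawal for a clinically significant laboratory value. SAP Sections 6.4 and 19.2 expect retests, unscheduled measurements and extra testing to evaluate an adverse event. The label in Appendix 4 asks for blood counts before each dose but for the liver only says to monitor, which may explain the different treatment.

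Most of this stands, and it rules out the stronger reading. A reader might infer that the ALT/AST and B-cell rules cannot be applied at all. The documents do not support that, because nothing prevents a site from having the result. What survives is that permission is not a requirement. Section 6.3.5 contains the general sentence on local testing and still adds explicit pre-dose conditions for the CBC and the pregnancy test. The label's distinction does not settle the matter either, because the protocol chose to put ALT/AST under the same rule as the counts.

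A reader might also infer that three of four doses are compromised in every subject. The gaps in Step 2 do exist for everyone, but the rule operates only after ALT/AST exceeds 5 times ULN. Subjects above 1.5 times ULN at screening are excluded, and the documents give no frequency for such elevations in this population.

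On the B-cell count, screening is timed so that results arrive before enrollment, repeats are allowed within the screening window, and eligibility is confirmed on Day 1 before dosing. That leaves few cases, and one such subject would not show that a cohort's pharmacodynamic data are confounded.

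**Conclusion.** The point holds in a limited form. Application of the ALT/AST limb of Section 4.4.4 is not assured, though it is not prevented. The gap arises when a subject with a Grade 3 or higher elevation is still above Grade 1 at the last interim sample, 7 days before dose 2 or 14 days before doses 3 and 4 (3 to 11 and 10 to 18 days with windows). The number of subjects concerned cannot be estimated from the documents and may be small.

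The conclusion assumes that a site does what the schedule requires and no more, and that the central laboratory result is not back on the day of the draw. No turnaround time is stated. This is a clarification worth making because it touches a safety stopping rule and is cheap, but it does not undermine the design. The B-cell point is secondary and minor.

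**What to change.** Reconcile the ALT/AST limb of Section 4.4.4 with the pre-dose result notes in Sections 4.3.2.2.4, 4.3.2.2.6, 4.3.2.2.8 and 6.3.5 and with Table 3 footnotes c and e, so that the evidence the rule relies on is in hand when the rule is applied. How to do this is for the sponsor to decide, and the thresholds are not in question. As a minor companion edit, reconcile Exclusion 8d and Table 3 footnote d with the Day 1 note in Section 4.3.2.1 for previously B-cell-depleted subjects with no normal count before Day 1.

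The cost is protocol wording and possibly a short wait for a result, which the protocol already accepts for the CBC.
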